Table 2	Schedule of Assessments: Cohorts 1 and 2 – Subjects Receiving Booster Dose	17
Table 3	Schedule of Assessments: Cohorts 3, 4, and 6.....	20
Table 4	Dosing and Administration	44
Table 5	Probability (%) of Detecting at Least 1 Adverse Event Under Different Incidence Rates	61

LIST OF FIGURES

Figure 1	Study Flow Chart	36
----------	------------------------	----

LIST OF ABBREVIATIONS

ACE-2	Angiotensin-Converting Enzyme 2
ADE	Antibody-Dependent Enhancement
AE	Adverse Event
AESI	Adverse Event of Special Interest
ALP	Alkaline Phosphatase
ALT	Alanine Aminotransferase
aPTT	Activated Partial Thromboplastin Time
AST	Aspartate Aminotransferase
BMI	Body Mass Index
BP	Blood Pressure
CFR	Code of Federal Regulations
ChAd	Chimpanzee Adenovirus
CI	Confidence Interval
CK	Creatine Kinase
CLIA	Clinical Laboratory Improvement Amendments
CMP	Clinical Monitoring Plan
COVID-19	Coronavirus Disease 2019
CRO	Contract Research Organization
CRP	C-Reactive Protein
CSR	Clinical Study Report
DCC	Data Coordinating Center
DCF	Data Collection Form
DLT	Dose-Limiting Toxicity
DNA	Deoxyribonucleic Acid
E	Envelope (Protein)
EC	Ethics Committee
ECG	Electrocardiogram
eCRF	Electronic Case Report Form
ELISpot	Enzyme-Linked Immunospot
ESR	Erythrocyte Sedimentation Rate
EUA	Emergency Use Authorization
GCP	Good Clinical Practice
GMFR	Geometric Fold-Rise
GMT	Geometric Mean Titer
Hb	Hemoglobin
HBsAg	Hepatitis B Surface Antigen
HCV	Hepatitis C Virus
HIV	Human Immunodeficiency Virus

IATA	International Air Transport Association
IB	Investigator's Brochure
ICF	Informed Consent Form
ICH	International Council for Harmonisation
■■■■■	■■■■■
IFN	Interferon
IgA	Immunoglobulin A
IgG	Immunoglobulin G
IgM	Immunoglobulin M
IM	Intramuscular
IND	Investigational New Drug Application
INR	International Normalized Ratio
IV	Intravenous
LNP	Lipid Nanoparticle
M	Membrane (Protein)
MAAE	Medically Attended Adverse Event
MedDRA	Medical Dictionary for Regulatory Activities
MERS-CoV	Middle East Respiratory Syndrome Coronavirus
MHRA	Medicines and Healthcare Products Regulatory Agency
MOP	Manual of Procedures
mRNA	Messenger Ribonucleic Acid
N	Nucleocapsid (Protein) or Number of Subjects
NHP	Non-Human Primate
NOCMCs	New Onset Chronic Medical Conditions
PBMCs	Peripheral Blood Mononuclear Cell
PCR	Polymerase Chain Reaction
PEG	Polyethylene Glycol
PI	Principal Investigator
PIMMCs	Potentially Immune-Mediated Medical Conditions
PLT	Platelets
PT	Prothrombin Time
QA	Quality Assurance
QC	Quality Control
RBD	Receptor-Binding Domain
RNA	Ribonucleic Acid
S	Spike
SAE	Serious Adverse Event
SAM	Self-Amplifying mRNA
SAP	Statistical Analysis Plan

SARS-CoV-2	Severe Acute Respiratory Syndrome Coronavirus 2
SGP	Subgenomic Promoter
SIV	Simian Immunodeficiency Virus
SNP	Single Nucleotide Polymorphism
SOC	System Organ Class
SOP	Standard Operating Procedure
SUSAR	Suspected Unexpected Serious Adverse Reactions
TCE	T-cell Epitope(s)
Th1	T Helper Cell Type 1
Th2	T Helper Cell Type 2
UK	United Kingdom
US	United States
UTR	Untranslated Regions
VAERD	Vaccine-Associated Enhanced Respiratory Disease
VEEV	Venezuelan Equine Encephalitis Virus
Vp	Viral Particle(s)
WBC	White Blood Cell

3 PROTOCOL SUMMARY

3.1 Synopsis

Protocol Title	A Phase 1 Trial to Evaluate the Safety, Immunogenicity, and Reactogenicity of a Self-Amplifying mRNA Boost Prophylactic Vaccine Against SARS-CoV-2 in Previously Vaccinated Healthy Adults 18 Years and Older
Trial Centers	Multi-center trial in the United Kingdom
Clinical Phase	Phase 1
Study Design	Open-label, multiple cohort, dose-escalation vaccine study
Study Population	Healthy adults 18 years and older
Sample Size	
This study will enroll 50 volunteers as follows:
 
• Cohort 1 (N=10, including 2 sentinels): 10 mcg GRT-R910 (after AstraZeneca) 2 doses, homologous prime-boost, booster dose will be 113 days (16 weeks) after the prime for adults ≥ 60 years of age.• Cohort 2 (N=10, including 2 sentinels): 30 mcg GRT-R910 (after AstraZeneca) 2 doses, homologous prime-boost, booster dose will be 113 days (16 weeks) after the prime for adults ≥ 60 years of age.• Cohort 3 (N=10): 10 mcg GRT-R910 (dose selected from Cohorts 1 and 2) after adenovirus-based vector vaccine, homologous prime-boost, booster dose will be 28 days after the prime for adults ≥ 60 years of age.• Cohort 4 (N=10): 10 mcg GRT-R910 (dose selected from Cohorts 1 and 2) after messenger ribonucleic acid (mRNA) vaccine, homologous prime-boost, booster dose will be 28 days after the prime for adults ≥ 60 years of age.• Cohort 6 (N=10): 10 mcg GRT-R910 (dose selected from Cohorts 1 and 2) after mRNA vaccine, homologous prime-boost, booster dose will be 28 days after the prime for adults ≥ 18 to ≤ 59 years of age. 
Sentinel dosing in Cohorts 1 and 2 will consist of 2 volunteers in each cohort dosed 72 hours ahead of the remainder of each cohort, with the remainder of the volunteers dosed at the same dose level only if no halting rules are met. Enrollment in Cohort 2 will only proceed if safety data from all volunteers in Cohort 1 meet the dose-escalation rules. Injection will be given intramuscularly as a prime-boost at least 2 months after the last administration of a severe acute respiratory syndrome coronavirus 2 (SARS-CoV-2) vaccine either approved for emergency supply or approved for use by the Medicines and Healthcare Products Regulatory Agency (MHRA) for prevention of SARS-CoV-2. Subjects should refrain from a subsequent boost with an emergency supply or approved SARS-CoV-2 vaccine for a minimum of 4 months after the second dose of study vaccine.

Follow-up Duration	For Cohorts 1 and 2 (NOT receiving booster dose): 12 months For Cohorts 1 and 2 (receiving booster dose): 16 months For Cohorts 3 and 4: up to 13 months For Cohort 6: 7 months
Primary Objectives	
• To assess the safety and tolerability of 2 different doses (10 or 30 mcg) of GRT-R910 when administered to healthy adults (≥ 60 years of age) who were previously vaccinated with a first-generation Coronavirus Disease 2019 (COVID-19) vaccine (Cohorts 1 and 2; AstraZeneca)• To assess the safety and tolerability of a 10 mcg dose of GRT-R910 when administered to healthy adults (≥ 18 years of age) who were previously vaccinated with an mRNA-based COVID-19 vaccine (Pfizer/BioNTech, Moderna)

Primary Outcome Measures	
Occurrence of solicited local reactogenicity signs and symptoms for 7 days after GRT-R910 vaccinationOccurrence of solicited systemic reactogenicity signs and symptoms for 7 days after GRT-R910 vaccinationOccurrence of unsolicited adverse events (AEs) for 28 days after last study-administered GRT-R910 vaccinationChange from baseline for clinical safety laboratory parameters 7 days after last study-administered GRT-R910 vaccinationOccurrence of serious adverse events (SAEs) and adverse events of special interest (AESIs), including potentially immune-mediated medical conditions (PIMMCs), medically attended adverse events (MAAEs), and new onset chronic medical conditions (NOCMCs), throughout the entire study after GRT-R910 vaccination
Secondary Objective	
To assess the cellular and humoral immunogenicity of GRT-R910 when administered to volunteers (≥ 60 years of age for Cohorts 1, 2, 3, and 4 and ≥ 18 to ≤ 59 years of age for Cohort 6) who were previously vaccinated with either an adenoviral COVID-19 vaccine (AstraZeneca, Janssen) or an mRNA-based COVID-19 vaccine (Pfizer/BioNTech, Moderna)
Secondary Outcome Measures	
Response rate, and magnitude of SARS-CoV-2-specific antibody binding and neutralization in serum samplesResponse rate, magnitude, and breadth of SARS-CoV-2 specific T-cells as assessed by interferon (IFN)-γ enzyme-linked immunospot (ELISpot) in 10 subjects per cohort
	[REDACTED]

Rationale

This Phase 1 clinical trial will explore, in vaccinated subjects 18 years and older, the ability of a self-amplifying mRNA (SAM; GRT-R910) vaccine to boost and expand, beyond Spike, the immunogenicity of AstraZeneca's AZD1222 (Covishield[®], Vaxzevria[®]; referred to as AstraZeneca vaccine), JNJ-78436735 (the Janssen COVID-19 Vaccine; referred to as the Janssen vaccine), Moderna (Spikevax[®]; referred to as the Moderna vaccine), and Pfizer/BioNTech (Comirnaty[®]; referred to as the Pfizer vaccine) COVID-19 antigenic vaccines. GRT-R910 uses a novel codon optimized Spike cassette with additional T-cell epitopes (cassette S-TCE) to safely drive strong, broad, and durable B- and T-cell immune responses to SARS-CoV-2.

Overall Design

This is a multi-center, open-label, dose-escalation design study to examine dose, safety, tolerability, and immunogenicity of GRT-R910, an investigational SAM SARS-CoV-2 vaccine when administered to healthy adults 18 years and older who were previously vaccinated with a first-generation COVID-19 vaccine (Cohorts 1 and 2; AstraZeneca), an adenoviral COVID-19

vaccine (Cohort 3; AstraZeneca, Janssen), or an mRNA-based COVID-19 vaccine (Cohorts 4 and 6; Pfizer/BioNTech, Moderna).

In Cohorts 1 and 2, healthy adults ≥ 60 years of age (N=10, including 2 sentinels per cohort) will receive 2 doses of GRT-R910 (homologous prime-boost) at 1 of 2 dose levels (10 mcg or 30 mcg) at least 2 months after receiving AstraZeneca's COVID-19 prime and boost vaccine. The GRT-R910 booster dose will be administered 113 days (16 weeks) after the prime. In Cohorts 3 and 4, healthy adults ≥ 60 years of age (N=10) will receive 2 doses of GRT-R910 (homologous prime-boost) 10 mcg (dose selected from Cohorts 1 and 2) at least 2 months after receiving an adenoviral COVID-19 vaccine (Cohort 3; AstraZeneca, Janssen), or an mRNA-based COVID-19 vaccine (Cohort 4; Pfizer/BioNTech, Moderna). In Cohort 6, healthy adults ≥ 18 to ≤ 59 years of age (N=10) will receive 2 doses of GRT-R910 (homologous prime-boost) 10 mcg (dose selected from Cohorts 1 and 2) at least 2 months after receiving an mRNA-based COVID-19 vaccine (Pfizer/BioNTech, Moderna). The GRT-R910 booster dose will be administered 28 days after the prime.

Sentinel dosing in Cohorts 1 and 2 will consist of 2 volunteers in each cohort dosed 72 hours ahead of the remainder of each cohort, with the remainder of the volunteers dosed at the same dose level only if no halting rules are met. Enrollment in Cohort 2 will only proceed if safety data from all volunteers in Cohort 1 meet the dose-escalation rules. There will be no sentinel dosing in Cohorts 3, 4, and 6. The dose for Cohorts 3, 4, and 6 was selected from Cohorts 1 and 2 after evaluation of reactogenicity, safety, and initial immunogenicity. Dose selection will be determined by the Gritstone clinical team in consultation with the Principal Investigator(s).

The reactogenicity and immunogenicity data assessed after the first dose of GRT-R910 will inform selection of the GRT-R910 dose to be tested in future studies. The 10 mcg dose of GRT-R910 was selected for use in Cohorts 3, 4, and 6 by evaluating the balance of immunogenicity and reactogenicity of a single dose of GRT-R910 in Cohorts 1 and 2.

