12.2 Sample Size Considerations

The targeted sample size for each of the study cohorts was determined based on previous Phase 1 studies. Recruitment for GRT-R910 boost vaccination schedules will target enrolling 50 volunteers as follows:

- Cohort 1 (N=10, including 2 sentinels): 10 mcg GRT-R910 (after AstraZeneca) 2 doses, homologous prime-boost, booster dose will be 113 days (16 weeks) after the prime for adults ≥ 60 years of age.
- Cohort 2 (N=10, including 2 sentinels): 30 mcg GRT-R910 (after AstraZeneca) 2 doses, homologous prime-boost, booster dose will be 113 days (16 weeks) after the prime for adults ≥ 60 years of age.
- Cohort 3 (N=10): 10 mcg GRT-R910 (dose selected from Cohorts 1 and 2) after adenovirus-based vector vaccine, homologous prime-boost, booster dose will be 28 days after the prime for adults ≥ 60 years of age.
- Cohort 4 (N=10): 10 mcg GRT-R910 (dose selected from Cohorts 1 and 2) after mRNA vaccine, homologous prime-boost, booster dose will be 28 days after the prime for adults ≥ 60 years of age.
- Cohort 6 (N=10): 10 mcg GRT-R910 (dose selected from Cohorts 1 and 2) after mRNA vaccine, homologous prime-boost, booster dose will be 28 days after the prime for adults ≥ 18 to ≤ 59 years of age.

Sample size and power analysis for safety

The goal of the safety evaluation for this study is to identify safety concerns associated with product administration. The ability of the study to detect SAEs (see [Section 11.1.2](#)) can be expressed by the true event rate above which at least 1 SAE would likely be observed.

For each group of 10 subjects, there is an 89% chance of observing at least 1 event if the true rate is 20% or higher.

Binomial probabilities of observing at least 1 event among groups of size 10, 20, or 30 overall are presented in [Table 5](#) for a range of possible true adverse event rates. These calculations provide a more complete picture of the sensitivity of the study design to identify potential safety problems with the vaccine.

Table 5 Probability (%) of Detecting at Least 1 Adverse Event Under Different Incidence Rates

Incidence Rate (%)	Sample Size = 10	Sample Size = 20	Sample Size = 30
0.01	0.10	0.20	0.30
0.1	1.00	1.98	2.96
1.0	9.56	18.21	26.03
2.0	18.29	33.24	45.45
5.0	40.13	64.15	78.54
10.0	65.13	87.84	95.76
20.0	89.26	98.85	99.88

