12.4 Final Analysis Plan

This section describes the final study analyses. All safety data from enrolled subjects will be analyzed according to dose cohort and overall. In the rare instance that a participant receives the wrong treatment at a specific study product administration time, the statistical analysis plan (SAP) will address how to analyze the participant's safety data. The Safety Analysis Population will include all subjects who received any dose of GRT-R910.

The Clinical Study Report (CSR) will be completed when all primary and secondary safety, clinical, and immunological endpoint data are available. Any available data from the exploratory endpoints may also be included. Additional exploratory endpoint data may be included in an addendum to the CSR, publication of manuscript(s), or other report. The primary analysis of immunogenicity (secondary) endpoints will use the immunogenicity analysis population, defined as individuals who receive GRT-R910 at the expect dose level within the expected visit window and with at least some post-dose immunogenicity data.

No formal multiple comparison adjustments will be employed for multiple primary or secondary endpoints. However, multiplicity adjustments will be made for certain primary or secondary endpoint assays, as discussed below, when the assay endpoint is viewed as a collection of

hypotheses (e.g., testing multiple pseudo-viruses to determine a positive antiviral functional activity response). Unless otherwise noted, 95% confidence intervals will be calculated. Any statistical tests will be 2-sided and will be considered statistically significant if the p-value is below 0.05.

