Only TEAEs will be included in summary tables and will be summarized by cohort and vaccination (Vaccination Dose 1, Vaccination Dose 2, entire study period). Percentages will be based upon the number of participants in the Safety Analysis Set within each cohort. A subject may have more than 1 AE for an SOC or PT. A subject with 2 or more AEs within the same level of summarization will be counted only once in that level 1

The rules described in [Table 4](#) will be applied for AEs partial dates during this study to understand if it is TEAE. No other data will be imputed.

All AEs will be reported by data listings for the SAF.

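### Forty of 50 subjects receive 10 mcg, but the plan specifies no pooled 10 mcg safety column and none for the population of the second primary objective

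*Protocol*

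**What the plan says.** Protocol 12.2 sets out five cohorts of 10:

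- "Cohort 1 (N=10, including 2 sentinels): 10 mcg GRT-R910 (after AstraZeneca) 2 doses, homologous prime-boost"
- "Cohort 2 (N=10, including 2 sentinels): 30 mcg GRT-R910 (after AstraZeneca) 2 doses, homologous prime-boost"
- "Cohort 3 (N=10): 10 mcg GRT-R910 (dose selected from Cohorts 1 and 2) after adenovirus-based vector vaccine"
- "Cohort 4 (N=10): 10 mcg GRT-R910 (dose selected from Cohorts 1 and 2) after mRNA vaccine"
- "Cohort 6 (N=10): 10 mcg GRT-R910 (dose selected from Cohorts 1 and 2) after mRNA vaccine"

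Cohorts 1 to 4 are aged 60 or over; Cohort 6 is aged 18 to 59. The second dose comes at 113 days in Cohorts 1 and 2 and at 28 days in Cohorts 3, 4 and 6.

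On grouping, Protocol 12.4 states: "All safety data from enrolled subjects will be analyzed according to dose cohort and overall". SAP 4 makes by-cohort summaries the default for categorical data. SAP 9.1 summarises treatment-emergent events by cohort and vaccination and adds: "Percentages will be based upon the number of participants in the Safety Analysis Set within each cohort". SAP 9.1.1.1 and 9.1.1.2 switch to 'treatment group' plus a total. SAP 9.1.2 (solicited events) uses 'treatment group' for the tabulation and 'vaccination group' for the denominator. None of these terms is defined. The lead text of SAP 9 presents safety data by the treatment actually received at the prime and by the booster dose actually received.

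The second primary objective begins "To assess the safety and tolerability of a 10 mcg dose of GRT-R910 when administered to healthy adults" (Protocol 3.1), and its population differs between the documents. Protocol 3.1 and 5 limit it to mRNA-vaccinated subjects; SAP 2 extends it to adenoviral or mRNA vaccination.

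**The concern.** Both primary objectives are expressed by dose, and Protocol 12.1 gives the aim as preliminary estimates of the safety and reactogenicity of different doses. The grouping that is spelled out is the single cohort, so a 10 mcg event rate would be read from rows of 10 subjects although 40 receive that dose at the prime. The group that is explicitly larger, the protocol's overall, combines 40 subjects at 10 mcg with 10 at 30 mcg and so estimates the rate at neither dose unless the two rates are equal. The same holds for any all-subject total in SAP 9.1.1.1 and 9.1.1.2.

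Two things are at stake. One is precision that the data already contain and the tables may not show. The other is reproducibility: with 'treatment group' undefined, two programmers could build different primary safety tables from the same SAP, one with five cohort columns and one with two dose columns.

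**Working it through.** **1. The plan's own figure.** Protocol 12.2 (Table 5) and SAP 4.3 (Table 3) give P(at least one event) = 1 − (1 − p)^n. For n = 10 and p = 0.20: 1 − 0.80^10 = 89.26%, matching the stated 89%. All 21 cells of the table reproduce to two decimals. It covers n = 10, 20 and 30, but no adverse event summary is specified for a group of 20 or 30.

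**2. Subjects per dose (Protocol 12.2 and Table 4).**

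| Group | Cohorts | Planned n |
|---|---|---|
| 10 mcg, after prime | 1+3+4+6 | 40 |
| of these, aged 60 or over | 1+3+4 | 30 |
| of these, aged 18–59 | 6 | 10 |
| 10 mcg, after 28-day booster | 3+4+6 | up to 30 |
| Second objective, protocol wording | 4+6 | 20 |
| Second objective, SAP wording | 3+4+6 | 30 |
| 30 mcg | 2 | 10 |

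The SAP row leaves out Cohort 1 because the first objective names it. Under the protocol wording, Cohort 3 falls under neither primary objective.

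**3. Zero events.** The exact (Clopper-Pearson) two-sided 95% upper limit is 1 − 0.025^(1/n).

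| n | Upper limit |
|---|---|
| 10 | 30.8% |
| 20 | 16.8% |
| 30 | 11.6% |
| 40 | 8.8% |

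**4. Common events.** Exact 95% intervals at assumed observed rates:

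| Observed rate | n = 10 | n = 40 |
|---|---|---|
| 30% | 3/10: 6.7–65.2% (58.6 points wide) | 12/40: 16.6–46.5% (30.0 points wide) |
| 50% | 5/10: 18.7–81.3% | 20/40: 33.8–66.2% |

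At 30%, 6/20 gives 11.9–54.3% and 9/30 gives 14.7–49.4%.

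**5. Detection at a true 5% rate.** n = 10: 1 − 0.95^10 = 40.1%. n = 40: 1 − 0.95^40 = 87.1%.

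**6. The mixed-dose total (assumed rates).** Overall = (40 × p10 + 10 × p30)/50.

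- 20% at 10 mcg and 50% at 30 mcg: (8 + 5)/50 = 26%.
- 30% and 60%: (12 + 6)/50 = 36%.
- Equal rates: no distortion.

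**7. The same check on a pooled 10 mcg column.** Assume 20% in the 30 older subjects and 50% in the 10 younger ones: (6 + 5)/40 = 27.5%, the rate of neither age group. A 10 mcg column therefore needs an age split.

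**8. The grouping rules side by side.**

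- Protocol 12.4: dose cohort and overall.
- SAP 4 and 9.1: cohort.
- SAP 9, lead text: actual prime treatment, actual booster dose.
- SAP 9.1.1.1 and 9.1.1.2: undefined treatment group, plus total.
- SAP 9.1.2: undefined treatment group and vaccination group.

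No entry names a pooled 10 mcg column. The lead text of SAP 9 yields one only if it sets the table columns, which contradicts SAP 4 and 9.1. It may instead only be an as-treated rule, like the one in SAP 4.5.3.

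**The case against.** A reader might infer that no planned safety summary groups by dose and that the overall column is the only pooled one. The documents do not support either claim. The planned doses are only 10 and 30 mcg, so the lead text of SAP 9, read literally, is a grouping by dose. SAP Table 9 also has laboratory, vital-sign, ECG and biomarker tables restricted to Cohorts 3, 4 and 6. Any total there would be 10 mcg only, although none is specified and those tables do not cover adverse events. Their separation from Cohorts 1 and 2 also follows from different visit schedules.

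A second objection concerns pooling itself. Protocol 4.3 expects lower reactogenicity in older adults. The 10 mcg cohorts also differ in prior vaccine and in the prior-infection exclusions (Protocol 7.2: any confirmed COVID-19 for Cohorts 1 and 2; only within 112 days for the others). This stands, and it is why the n = 40 column must be split by age and remain supplementary.

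A third objection concerns consequences. The study is descriptive. The 10 mcg dose for Cohorts 3, 4 and 6 was chosen from Cohorts 1 and 2, so these columns could not have changed that choice. Cohort counts can be added by hand, so no data are lost and no cohort estimate is biased. This too stands and limits the severity. It does not resolve the conflicting rules or supply the exact intervals for a combined group.

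**Conclusion.** The point holds as a cheap improvement. The plan specifies no pooled 10 mcg column and none for the second primary objective's population, whether that is 20 subjects (protocol) or 30 (SAP). The rules that might imply a dose grouping conflict or rest on undefined terms.

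For an event not seen at all, the exact upper limit falls from 30.8% in a single cohort to 8.8% across all 10 mcg subjects after the prime. At an assumed 30% observed rate, the interval width about halves, from 58.6 to 30.0 points. These sizes assume full enrolment and treat the pooled cohorts as one population, which is only an approximation. The dilution figures rest on assumed rates. After the booster, pooling is reasonable only for the 28-day cohorts: Cohort 1 is boosted at 113 days and some of its subjects may take a single dose (Protocol 4.3.1, SAP 7.2).

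A reader might go further and conclude that the overall column invalidates the safety analysis. It does not: the protocol shows it alongside the cohorts, so the doses stay separated there.

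**What to change.** 1. Define 'treatment group' and 'vaccination group' in the SAP, and reconcile Protocol 12.4 with SAP 4, 9, 9.1, 9.1.1.1, 9.1.1.2 and 9.1.2. State whether the lead text of SAP 9 sets table columns or is only an as-treated rule.
2. Reconcile the second primary objective between Protocol 3.1 and 5 and SAP 2.
3. In the solicited and unsolicited adverse event tables, keep the cohort columns and add, with exact 95% intervals:
   - (a) all 10 mcg after the prime (Cohorts 1+3+4+6, n = 40), also split into 60 or over (Cohorts 1+3+4, n = 30) and 18–59 (Cohort 6, n = 10);
   - (b) 10 mcg after the 28-day booster (Cohorts 3+4+6, up to n = 30), with the same age split (Cohorts 3+4, up to 20; Cohort 6, up to 10);
   - (c) the population of the second primary objective as reconciled in step 2.
4. Label any all-subject total as mixed-dose and do not report it as the safety rate of either dose.

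The cost is SAP wording, an aligned sentence in the protocol and extra table columns; no new data are needed. The drawback is that the pooled columns combine cohorts that differ in age, prior vaccine and prior-infection criteria, so they should be labelled supplementary.
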